3.2.4. Spontaneous Oxygen Desaturation During Sleep

Functional residual capacity (FRC) is dynamically determined during the first year of life,⁷⁷ and the volume of O2 available in the lung will be at its nadir at the end of tidal exhalation. Whether or not pauses in breathing, with stable or falling end-expiratory volume, cause desaturation will be closely linked to the volume of the dynamically determined FRC. Even brief pauses in breathing may result in small drops in oxyhemoglobin saturation (Figure 3.2.5). This critical relationship was shown in a recent study measuring FRC by washout techniques and analyzing central apneas in 36-week PMA infants.⁴² With apneas as short as 6 to 7 seconds, some infants had falls in SpO2% of ~ 7%. The short apneas did not cause desaturation events in all infants, but the lower the FRC, the higher the frequency of apneas with desaturation (P < 0.001). The effects of smaller FRC, or end-expiratory volume (EEV), were greater during active sleep, and 28 of 29 infants had apnea with desaturation events > 5% during active sleep (33.3 + 29.2 desaturations / hr). These observations suggest that mild oxyhemoglobin desaturations

resulting from brief apneas may be a marker for impaired respiratory function and lower FRC.

Figure 3.2.5. Recording of respiratory effort, airflow, and SpO₂ in a sleeping infant who was born at 28 weeks. Child is breathing room air at a rate of 20 breaths per minute . A 9 second apnea, the equivalent of 3 respiratory cycles, is followed by a fall in SpO₂% from 98% to 92%.

Oxyhemoglobin desaturation events during sleep will be studied during RIP, and the same eligibility criteria and risks apply as for RIP. After placing RIP bands and study oximeter measurements will be taken during feeding (see section 3.2.4). The infant is allowed to fall

asleep after the feeding, and recordings of oxygen saturations and RIP measurements are performed one hour after feeding. The feasibility of this approach has been pre-tested at URUB.

3.3. Assessments During Follow-up to 1 Year Corrected Age

Research staff at the clinical PROP centers will obtain follow-up data from the infant's primary caregiver after the infant has been discharged from the hospital. This will require a significant investment of time and energy and is essential to characterize the respiratory status of study participants during the first year of life. We aim to achieve a very high retention rate of at least 90% and ideally > 95% to minimize ascertainment bias.

3.3.1. Data Collection at Months 3, 6, 9 and 12

At age 3, 6, 9, and 12 months corrected age (+ 1 month corrected age), the research staff at the clinical centers will contact the family to schedule and conduct an interview with the primary caregiver about the infant's health status. Contact information will be verified and revised as needed. A focused questionnaire will be administered over the telephone or in person at 3, 6, 9 and 12 months corrected age by the research staff to gather detailed data about hospitalizations for cardiopulmonary causes as well as for other medical reasons, respiratory medication use, respiratory symptoms and home technology dependence. For further details please refer to section 2.1

Medication used during the previous 3 months will be reported by parents to the site staff by listing them in advance of each follow-up call and reading them to the interviewer or by reading the labels to the interviewer at the time of the encounter. Exposure to environmental risk factors (young siblings, smoking, kerosene heater, pets) will also be recorded. Lastly, we will administer a symptom survey for gastroesophageal reflux disease (GERD) that was developed and validated for infants and children < 18 months by Orenstein and colleagues.⁷⁸ The 12-item questionnaire assesses symptoms associated with reflux over the past week.

3.3.2. Physical Examination at Month 12

During the in-person visit at 1 year corrected age, all infants will receive a standardized physical examination. A clinical scoring system was designed using measurements that (i) are commonly employed by practitioners and require no specialized equipment and that (ii) represent the underlying physiology and potential pathophysiology of the respiratory system. Scores like the Respiratory Distress Assessment Instrument (RDAI) have typically been used to demonstrate responses to interventions in wheezy infants.⁷⁹⁻⁸¹ Such scoring systems have been shown to be valid, responsive and have good inter-observer reliability. No such score, however, has been previously developed to track the respiratory courses of infants born prematurely. The PROP Physical Examination Score will use some elements of the RDAI, but incorporate other elements that reflect the effects of chronic respiratory impairment, such as growth and the development of digital clubbing. It has long been recognized that respiratory impairment and hypoxemia result in growth failure among infants with BPD.^{82, 83} In contrast, rapid weight gain has been associated with lower lung function and increased risk of wheezing illness over the first three years of life in healthy term infants.^{84, 85}

The PROP Physical Examination Score will be assessed at 36 or 40 weeks PMA, and again at 1 year corrected age. The infant will be evaluated during a period of quiet wakefulness. Weight will be measured with the infant unclothed, and length will be determined using an infant length board. Measurements of weight and length will be compared with published reference values and Z scores will be calculated. The respiratory rate will be counted over a full minute while the infant is breathing quietly. Assessment of retractions, accessory muscle use, and of thoraco-abdominal synchrony will be made with the infant in a recumbent or semi-recumbent position. Presence and distribution of crackles (none, isolated to 1 region, isolated to 2 regions, or diffuse) will be made by auscultation. Similarly, presence, timing (expiratory, inspiratory or both) and character of wheezing (none, monophonic, polyphonic, or mixed) will be made by auscultation under resting conditions, and again when the thorax and upper abdomen are gently manually compressed during exhalation by the examiner. The point of maximal cardiac impulse will be palpated, and absence or presence of digital clubbing will be visually assessed.

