2.1. Primary Outcome: Post-prematurity Respiratory Disease

The primary goal of the PROP studies (single center and multicenter protocols) is to identify biomarkers (biochemical, physiological and genetic) and clinical variables that are associated with and thus potentially predictive of pulmonary status in preterm infants up to 1 year corrected age. An objective and validated measure of pulmonary outcome at 1 year does not currently exist. Some promising measures are in development but not yet ready for use in a multi-center large clinical study. For example, reduced alveolar number is a key pathologic feature of BPD .²¹ Physiologically, this is reflected in decreased diffusion capacity of the lung to carbon monoxide (DLCO), and infants with BPD have lower DLCO compared to healthy full term controls.²² However, measurement of infant DLCO in a multi-center study is not feasible in PROP because of the lack of standardized equipment, the need for C¹⁸O instead of standard CO, and the need for a mass spectrometer to measure CO instead of a standard infrared sensor.²³

Moreover, the PROP investigators firmly believe that the burden of chronic respiratory illness on the infants and their families is of utmost importance. Therefore, we propose a composite primary outcome of morbidity that is based on serial parental reports of respiratory symptoms, medications, hospitalizations and dependence on technology during the first year of life.

Data collection for the outcome assessment will be based on interviews conducted with the infant's main caregiver at 3, 6, 9 and 12 months corrected age. The time frame for data collection is based on questions "since last contact." Numerous epidemiological studies of asthma have used parental or self report of symptoms, physician-diagnosed asthma and allergies, or the use of medications (which may abrogate symptoms) as critical outcomes.^{16, 24-26} Recent studies have most commonly employed the International Study of Asthma and Allergies in Childhood (ISAAC) questionnaire.²⁷ These studies have collected data regarding 1 year old children, although not children before one year of age. The questionnaire to be utilized in PROP has been modified from the Tucson Children's Respiratory Study (CRS)^{20, 28-31} and the Breathing Outcomes Study. The latter is an ancillary study for the NICHD Neonatal Research Network (NRN) Surfactant Positive Airway Pressure and Pulse Oximetry Trial (SUPPORT).

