Survey items selected for the determination of the primary outcome will be focused on the following four domains, with any positive response to any element identifying morbidity:

- 1. **Respiratory medications**: inhaled bronchodilators, inhaled steroids, systemic steroids, methylxanthines, diuretics, pulmonary vasodilators
- 2. Hospitalizations for cardiopulmonary causes: any hospitalization regardless of duration
- 3. Symptoms: any wheeze, cough without cold
- 4. **Home technology dependence**: use of home oxygen, ventilator or CPAP/BiPAP of any durations since last contact

A late death after a postmenstrual age of 36 weeks from cardio-respiratory failure will also meet the definition of PRD.

The primary outcome will be dichotomous, and defined as "No substantial post-prematurity respiratory disease" or "Post-prematurity respiratory disease." To be classified as having post-prematurity respiratory disease, infants must have a positive response in at least 1 of 4 morbidity domains during at least 2 separate parental interviews. Quarterly data collection up to 1 year corrected age will allow us to identify phenotypes based on the trajectory of post-prematurity respiratory disease and how these different trajectories predict later lung function and the diagnosis of asthma, if we continue to follow this cohort of children.

Follow up data from recently published randomized controlled trials and observational studies in similar but not identical populations of very preterm infants suggest that the incidence of this primary outcome will be at least 30% and possibly as high as 60%.³²⁻³⁵

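### Medication, one of the four PRD domains, is asked for a fixed previous 3 months, while the outcome interviews ask about the time since last contact; the two recall periods need reconciling

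*Protocol*

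**What the plan says.** - **Outcome interviews (Protocol 2.1).** Interviews take place at 3, 6, 9 and 12 months corrected age. "The time frame for data collection is based on questions" framed as since last contact. The fourth domain repeats that period: "use of home oxygen, ventilator or CPAP/BiPAP of any durations since last contact".
- **Medication is a PRD domain (2.1).** Domain 1 lists "inhaled bronchodilators, inhaled steroids, systemic steroids, methylxanthines, diuretics, pulmonary vasodilators", and any positive element counts.
- **PRD rule (2.1).** An infant needs a "positive response in at least 1 of 4 morbidity domains during at least 2 separate parental interviews". Section 4.2 restates this as two time frames of roughly 3 months each.
- **Data collection (3.3.1).** Interviews are due at the same four ages, each with a window of plus or minus "1 month corrected age), the research staff at the clinical centers will contact the family". The paragraph naming the outcome domains refers the reader to Section 2.1. The next paragraph then says: "Medication used during the previous 3 months will be reported by parents to the site staff".
- **Visit schedule (Section 6).** Medication use is recorded on the follow-up interview form.

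No sentence says which recall period governs the medication domain.

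**The concern.** A since-last-contact question divides follow-up into adjoining periods, so a short exposure belongs to one interview. A fixed 3-month look-back does so only if every gap between interviews is exactly 3 months. When a call comes early relative to the previous one, part of the time is asked about twice; when it comes late, part is never asked about.

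This matters because PRD turns on two positive interviews. If Section 3.3.1 is followed literally, one short course of a listed drug can be reported at two interviews and satisfy a rule evidently meant to show morbidity in two separate periods. Conversely, a genuine exposure after a late or missed call can be lost. The medication-exposure record promised in Section 3.1.2, from birth to one year corrected age, would have the same double counts and holes. The recall period is fixed when the parent is asked, so it cannot be repaired in the analysis unless dates were recorded.

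**Working it through.** The protocol gives no figure for this, so there is none to reproduce. The check is interval arithmetic on the stated schedule, then a simulation for scale.

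**Inputs from the protocol:** target ages 3, 6, 9 and 12 months; window ±1 month; look-back 3 months (all 3.3.1).

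**1. Range of gaps between consecutive interviews.**
- Shortest: (6 − 1) − (3 + 1) = 1 month.
- Longest: (6 + 1) − (3 − 1) = 5 months.
- The 6-to-9 and 9-to-12 gaps have the same range. On target the gap is 3 months.

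**2. Overlap and uncovered time.** Overlap = max(0, 3 − gap); uncovered = max(0, gap − 3).
- Gap 3: both are 0, and the two wordings agree.
- Gap 1 (interviews at 4 and 5 months): the look-backs cover months 1–4 and 2–5, so months 2–4 are asked about twice. A course at month 3 is positive at both interviews.
- Gap 5 (interviews at 2 and 7 months): the second look-back covers months 4–7, so months 2–4 are never asked about.

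**3. Missed interview.** Section 4.3.4 foresees missed surveys. If the 6-month interview is missed, the gap from 3 to 9 months is nominally 6, with range (9 − 1) − (3 + 1) = 4 to (9 + 1) − (3 − 1) = 8. Uncovered time is nominally 3 months, range 1 to 5.

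**4. First interview.** Take 40 weeks postmenstrual age as corrected age zero and 4.345 weeks per month. Discharge at 36 weeks is then 4/4.345 = 0.9 month before term. An on-time first interview falls 3.9 months after discharge, leaving 0.9 month unasked; one held at 4 months leaves 1.9; one held at 2 months (2.9 months after discharge) leaves none.

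**5. Scale.** Assumptions not in the protocol: interview dates are independent and uniform within ±w months, and one brief (point-in-time) course occurs at a uniform time between the first and last interviews.
- For w = 1, gap = 3 + D, with D triangular on (−2, 2). Mean overlap = mean uncovered time = ∫₀² d(2 − d)/4 dd = (1/4)(4 − 8/3) = 1/3 month per gap.
- First to last interview averages 9 months. An overlap lies just before the earlier of its two interviews, so only two of the three overlaps fall inside this span: 2 × 0.333/9 = 7.4%. All three uncovered stretches fall inside it: 3 × 0.333/9 = 11.1%.
- Simulating 400,000 infants, which uses each infant's actual span, gives:

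| Spread of dates | Counted twice | Missed |
|---|---|---|
| ±1 month | 7.7% | 10.8% |
| ±0.5 month | 3.8% | 5.5% |
| ±0.25 month | 1.9% | 2.7% |

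**6. After the fix.** With a since-last-contact question, the same point-in-time course is counted exactly once whatever the dates. For a 5-day course at ±1 month, double counting falls from 9.8% to 3.8% and missed courses from 8.5% to 0%. The remaining 3.8% are courses that straddle an interview date.

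**The case against.** The best defence is that Section 2.1 already governs. Section 3.3.1 refers to it, and the 3-month phrase comes in a sentence about how parents report drugs, by advance list or by reading labels. With quarterly calls it may simply be shorthand for the interval since the last one, and it may have been written for the medication-exposure aim. The follow-up form and the manual of procedures are not shown, so the question actually put to parents is unknown. This makes the misclassification conditional on the form following Section 3.3.1. It does not remove the conflict: both phrases stand in the current text, and the visit schedule puts medication on the same interview form.

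There is some mitigation. The secondary PRD definition in 4.3.4 has a category for three or more intervals, which one brief course cannot reach through overlap, because interviews two visits apart are at least 4 months apart. Section 4.6.4 calls the study hypothesis-generating. Neither changes the two-interval primary definition.

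Three stronger readings are tempting, and the protocol does not support them:
- *About 11% of short courses are double counted (0.33/3).* That ratio applies only to an interval followed by another interview. Nothing follows the 12-month interview, so only two of the three intervals qualify: 11.1% × 2/3 = 7.4%. Full uniform use of the window is itself an assumption.
- *That percentage is the rate of false PRD.* A false classification also requires that no other domain or course makes a second interview positive. Wheeze, cough without cold, hospitalization and home technology all count.
- *Site calling habits produce an apparent site effect and dilute predictor associations.* This is possible in principle, but the protocol offers no basis for estimating either.

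**Conclusion.** The inconsistency is real and concerns how one domain of the primary outcome is ascertained. The 1-to-5-month gaps, the up to 2 months asked twice or not at all, the 1 to 5 months lost after a missed interview, and the shortfall at an on-time first interview for infants discharged before term follow from the protocol's schedule, taking term as corrected age zero. They apply if the 3-month look-back is used as written.

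The percentages (about 8% counted twice and 11% missed at full window use; about 4% and 5.5% at ±0.5 month) rest on assumed uniform, independent interview dates and describe a single brief course. They are not error rates for PRD, whose net change cannot be computed because it depends on the other domains.

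The two wordings coincide between interviews held exactly 3 months apart. I rate this a moderate inconsistency to reconcile, not a must-fix failure of the primary outcome.

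**What to change.** In Section 3.3.1, replace the previous-3-months wording with *since last contact (since discharge at the first interview)*, so that all four domains share the period Section 2.1 already sets. Have the interviewer give the parent the date of the last contact.

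Recording start and stop dates for each drug is optional. It would identify courses that straddle an interview, which count twice under either wording.

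The change is one phrase in the protocol, with the follow-up form to match if it uses the 3-month wording. The cost is longer parental recall whenever a gap exceeds 3 months: up to 5 months between on-window interviews and up to 8 after one missed interview. After a missed interview, one answer also covers two nominal intervals but counts as one positive interview.

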3.3.3. Infant Pulmonary Function Testing (iPFT)

Objective measures of lung function are critical for achieving the PROP goal of identifying novel mechanisms and associated functional and molecular biomarkers of respiratory disease risk in preterm infants. Diminished lung function is a risk factor for symptomatic respiratory disease, such as wheezing.^{20, 29} Although a history of BPD is associated with lower lung function in infancy and childhood,¹⁵ preterm infants without a history of BPD demonstrate airflow obstruction and gas trapping compared to normal controls.⁸⁶ These observations suggest factors other than BPD, or not captured by the current definitions of BPD, are involved in lung growth and repair following preterm birth. Previous studies of infant lung function after discharge from the NICU have involved small numbers of infants from single centers,^{41, 87} PROP will study a large cohort of neonates from multiple centers, and infant PFTs will provide crucial objective physiologic outcome measures for this unique study population.

Measurement of forced expiratory flows in infants began with the pioneering work of Wohl, Taussig, Landau, and others in the 1970's.^{88, 89} In these early studies, partial flow volume curves were generated at end expiration during tidal breathing by rapid thoracoabdominal compression (RTC) using a rapidly inflating jacket that surrounded the infant's chest and abdomen. The primary measure used was the maximal flow at functional residual capacity (V'_{maxFRC}). This technique was successfully used to demonstrate reduced expiratory flows in infants with BPD and cystic fibrosis.^{90, 91} Young infants with low V'_{maxFRC} prior to the onset of any respiratory illness are at increased risk for wheezing in the first 3 years of life.⁹²

Despite the insights gained from the RTC technique, there are some potential limitations with this method. FRC in infants is dynamically maintained and also affected by underlying lung disease.⁹³⁻⁹⁵ Hence, there may be some variability and instability in measuring flows around this landmark. Furthermore, the RTC technique does not allow measurement of fractional lung volume measures such as residual volume (RV) and total lung capacity (TLC). To overcome these limitations, investigators in the 1990's developed the raised volume rapid thoracoabdominal compression technique (RVRTC).⁹⁶⁻⁹⁸ In RVRTC, the infant's lungs are inflated to a pressure of 20-30 cmH₂O using a facemask sealed with therapeutic putty. This

allows measurements of forced expiratory flows starting at near TLC down to RV. RVRTC has been shown to be more sensitive than RTC alone in detecting airflow obstruction in infants with cystic fibrosis.²¹ Limited normal reference data are available.^{22, 23}

Two major developments have facilitated the use of RVRTC in a multicenter research setting. The first was the introduction of a commercially available device (nSpire Infant Pulmonary Lab (IPL), nSpire, Inc, Longmont, CO) which allows standardized equipment to be used at all study sites. The second was the development by the CF Foundation Therapeutics Development Network of a protocol for performing RVRTC and fractional lung volume measurements with the nSpire IPL and a quality control system to ensure capture of high-quality data. This system was recently applied to a multicenter study of lung function in infants with CF.⁹² Bronchodilator response in both normal infants and those with a history of BPD has been successfully measured using the RVRTC method.^{41, 98}

In PROP, we will use a standardized method of performing infant pulmonary function tests (PFTs) using the raised volume rapid thoracoabdominal compression (RVRTC) technique. Five sites have the capability to implement this protocol: Cincinnati Children's Hospital, UCSF, University of Rochester/University of Buffalo, Washington University and Duke/Indiana University.

Although our primary PFT measures will be derived from RVRTC, we will also measure V'_{maxFRC} and respiratory system compliance (Crs) and resistance (Rrs) because these measures are easier to obtain. Crs and Rrs will be obtained using the single breath occlusion method.

Our target sample size of at least 180 studies will represent the largest number of RVRTC PFTs in the preterm population and will allow us to study the relationship between lung function at 1 year of age and clinical and biologic factors associated with respiratory disease.

Infant pulmonary function testing for PROP will proceed in the following order:

- 1. Tidal breathing analysis (which includes Tpef/Te)
- 2. Crs and Rrs (compliance and resistance)
- 3. FRC measurement using whole body plethysmography
- 4. Forced expiratory flows from raised volumes (FVC, FEV0.5, FEF25-75, FEF75)
- 5. Fractional lung volumes (ERV, TLC, RV/TLC, FRC/TLC)
- 6. Bronchodilator response (Forced expiratory flows from raised volumes)

Parents will be approached for the iPFT before the infant reaches 12 months corrected age. An infant will be excluded from PF Testing for the following reasons:

- 1. History of adverse reaction or allergy to chloral hydrate sedation
- 2. Current symptoms of nasal obstruction or discharge
- 3. Clinically significant upper airway obstruction as determined by the Site Investigator (e.g. severe laryngomalacia, markedly enlarged tonsils, significant snoring, diagnosed obstructive sleep apnea)
- 4. Severe gastroesophageal reflux, defined as persistent frequent emesis despite antireflux therapy
- 5. Acute intercurrent respiratory infection, defined as an increase in cough, wheezing, or respiratory rate with onset in 2 weeks preceding visit
- 6. Hydrocephalus
- 7. Congenital heart disease

- 8. Severe neuromuscular disease
- 9. Any physical findings or conditions that would compromise the safety of the infant or the quality of the study data as determined by site investigator.

The parents of all eligible PROP participants will be asked to consider PF Testing. A separate consent form will be administered at the time of the test to explain the risks and benefits.

3.3.4. **Risks of iPFT**

Performing infant PFTs includes the use of moderate sedation with oral or rectal chloral hydrate (CH). Potential side effects of CH include respiratory depression, gastritis, and paradoxical agitation. All CH sedation will be performed under local institutional sedation policies, which include having appropriate monitoring and the presence of appropriately trained individuals present in the event of an untoward event.

The RVRTC technique itself is safe, with no adverse events reported in hundreds of tests. Although the maximum jacket pressure can be up to 120 cmH_2O , almost all of this pressure is absorbed by the chest wall. The device is FDA approved for use in infant PFTs, and the manufacturer's instruction for use will be strictly followed. In the recently completed CF infant PFT study,⁹² adverse events occurred in 44 out of 342 studies (12.8%), but only 3 events were severe. The most common adverse event was vomiting (29 events).

The 5 PROP clinical centers that will be performing IPFTs are very experienced in this technique and the overall serious adverse event rate (SAE) rate has been 1%. All SAEs have been related to sedation, and in most cases the infants had underlying conditions (e.g., obstructive apnea or neuromuscular disease) that increased their risk for respiratory compromise with CH therapy. Such infants would be excluded from iPFTs in PROP.

To assess bronchodilator response, infants will receive inhaled racemic albuterol. Albuterol is widely used in the clinical care of infants with a variety of respiratory diseases. Its safety profile is well known and well established. The common potential physical risks involved with albuterol therapy are mild, transient and easily reversed when the medication is discontinued. These include tachycardia, decreased serum potassium, decreased oxygen concentration, flushing, hyperactivity, prolonged cough and tremor. These risks are both dose dependent and cumulative. The risks during sedation may also include upper airway obstruction and the rare need for bag and mask ventilation due to reduced oxygen levels in the blood. Because our study design involves only receiving one dose of albuterol, these risks are lessened.

